3.3 STUDY HYPOTHESIS

We believe that the left inferior parietal lobule of the brain is a key region where inflammation and pain communicate in RA. Specifically, we hypothesise that inflammation leads to high levels of glutamate in the left inferior parietal lobule and subsequent haphazard functioning of this area. This then leads to abnormal communication with other regions of the brain such as those known to be important to pain processing in fibromyalgia. Ultimately, we expect these processes to alter patients' overall experience of pain.

If correct, we would expect a normalisation of left inferior parietal lobule activity to reduce glutamate levels and rebalance the functioning of the proposed pain systems in 'inflamed' RA patients.

4 STUDY OBJECTIVES

- 1) Determine the effects of L-IPL TMS on functional connectivity and neuronal signal cohesion.
- 2) Determine the effects of TMS on MRS Glutamate signal in the L-IPL.
- 3) Determine the effects of TMS on pain severity and disease activity in RA patients.

4.1 PRIMARY ENDPOINT

- Changes in functional connectivity and neuronal signal cohesion after TMS/sham therapy, as measured by 7T MRI
- Changes in glutamate signal in the L-IPL after TMS/sham therapy, as measured by 7T MRS

4.2 SECONDARY ENDPOINT(S)

Changes in components of sickness behaviour, pain severity, disease activity and inflammation after TMS/sham therapy as follows:

- Pain severity as measured by the Michigan Body Map Regional Pain and NRS-Pain
- RA disease activity as measured by SDAI, CDAI
- Sickness behaviour as measured by the Sickness Questionnaire

- Putative pain confounders as measured by PROMIS-Fatigue, PROMIS-Depression, PROMIS-Anxiety, PROMIS-Sleep Related Impairment, PROMIS-Physical functioning short form, PROMIS-Pain interference and ACR Fibromyalgia Scale
- Blood protein levels of inflammatory cytokines/chemokines

5 STUDY DESIGN

The study design is detailed below and is summarised in the STUDY FLOW CHART and **Error! Reference source not found.** The trial is a single-centre, randomised sham-controlled crossover study to test the hypothesis that normalisation of left inferior parietal lobule activity using TMS will reduce glutamate levels and rebalance the functioning of the proposed pain systems in 'inflamed' RA patients.

All of the study research data/ indices including the outcomes of study measures and samples will be shared with our collaborators in the University of Michigan. No personal data will be exported to our co-investigators at University of Michigan, but non-personal information may be transferred. The data transferred to the University of Michigan will include the study code/age/gender and questionnaire data. The University of Michigan will not have access to the pseudoanonymised key which will be kept within NHS GG&C only, therefore data will be anonymised to the University of Michigan investigators and pseudoanonymised to NHS GG&C/University of Glasgow investigators. The University of Michigan will undertake collaborative analyses; an appropriate Data Transfer Form and Controller to Controller Agreement will be completed.

5.1 STUDY POPULATION

The study will involve participants aged over 18 years with active inflammatory RA who meet the inclusion criteria below and who have none of the specified exclusion criteria. All will give full informed consent. Rheumatoid arthritis patients attending secondary care clinics in NHS GG&C and in NHS Lanarkshire will be screened for eligibility. NHS Lanarkshire will act as a participant identification centre (PIC) and all study participants will undertake study procedures at the University of Glasgow and the Queen Elizabeth University Hospital(NHS GG&C).

5.2 INCLUSION CRITERIA

- Adults \geq 18 years $<$ 75 years.
- Physician diagnosis of RA
- ACR definition of chronic widespread pain
- Able and willing to maintain usual/ medication for the 6-week study duration
- CRP $>$ 6mg/L or ESR $>$ 20mm/hr
- \geq 1 swollen joint
- Right-handed (to reduce neuroimaging heterogeneity)

5.3 EXCLUSION CRITERIA

- Inability to provide written informed consent.
- Severe physical impairment (e.g. blindness, deafness, paraplegia).
- Pregnant, planning pregnancy or breast feeding.
- Severe claustrophobia precluding MRI.
- Contraindications to MRI (e.g. metal implants/ pacemaker).
- Contraindication to TMS (e.g. history of seizures).

- Serious infection including sepsis, tuberculosis and opportunistic infections such as invasive fungal infections.
- Major confounding neurological disease including Multiple Sclerosis, Stroke, Traumatic Brain Injury, Parkinson's Disease, Alzheimer's Disease

5.4 CONCOMITANT MEDICATION

All Rheumatoid Arthritis therapies (including DMARDs/steroids/biologics) are permitted but must stay constant for the duration of the study. In exceptional circumstances, intra-articular/ intra-muscular steroids will be permitted according to investigator discretion.

5.5 IDENTIFICATION OF PARTICIPANTS AND CONSENT

Patients with active RA attending rheumatology outpatient clinics in NHS Greater Glasgow and Clyde and in NHS Lanarkshire will be notified of the study by the direct care team and will be provided with a patient information sheet. The patient will be asked to consent to a member of the research team contacting them by phone at least 24 hours later to gauge their interest in the study and allow them to ask any questions. This verbal agreement to be contacted by researchers will be documented by the direct care team in clinical record. Eligibility will be confirmed by a medically qualified doctor who is part of both the clinical/research team.

Contact details of interested patients will be shared by the clinical team with the research team via NHS to NHS email.

If the patient assents, they will be contacted by phone by a member of the research team to go through basic screening, address any queries, verify right hand dominance and check for MRI and significant medical condition contraindications. At this stage, potential participants will be invited to attend screening and consent visits that will be conducted at the Imaging Centre of Excellence (ICE) at the Queen Elizabeth University Hospital and the Centre for Cognitive Neuroimaging at the University of Glasgow. At these meetings, subjects will be asked again if they have any questions. Participants will undergo informed consent where two copies of the consent form will be signed (one each for the participant and the site file). A copy of the signed consent form will be inserted into the patient's record or scanned into the electronic patient record (EPR). A letter will be sent to the patient's GP informing them of their participation in the study.

Eligibility will be confirmed by a medically qualified investigator and consent will be taken by a member of the research team.

The research team comprises individuals who help to coordinate and perform the study in addition to individuals from the direct clinical care team. In addition to the clinical team, the research team requires access to the patient's medical record to be able to comprehensively collect necessary clinical characterization e.g blood results and validate patient reports.

5.6 RANDOMISATION & BLINDING

This is a randomised, sham-controlled, crossover study. Once participants have given consent and been fully screened for study eligibility, they will be randomised to receive either a single session of active TMS procedure to the L-IPL or a TMS sham procedure which will not modulate the brain. Provided the first session causes no reason to withdraw the participant, they will return 3 weeks later to receive the alternative TMS procedure to that they had undergone originally.

In order to optimise participant blinding, we will employ a sham coil which mimics the clicking and scalp sensations.

5.7 WITHDRAWAL OF PARTICIPANTS

The patient can decide to withdraw from the clinical trial at any time for no reason. The Chief Investigator (CI) or co-investigators also have the right to withdraw patients from the study if deemed in the best interests of the patient or in the event of Adverse Events (AEs), protocol violations, administrative or other reasons. Full details of withdrawal should be recorded on the electronic Case Report Form (eCRF).

Participants may decide to withdraw their initial consent for this study, at this point no further information regarding the participant will be collected. Data relating to the patient that has been collected up to the point of withdrawal will still be used. Any stored blood samples that can still be identified as the participants will be destroyed.

6 TRIAL PROCEDURES

6.1 STUDY SCHEDULE

The study will comprise of a total of 6 research visits.

6.1.1 Screening visit 1 (Day 0)

This screening visit will be conducted at the Queen Elizabeth University Hospital.

- Informed consent
- Review of inclusion / exclusion criteria
- Disease activity (SDAI / CDAI)
- 7T structural scans
- Randomisation
- Demographics
- BMI
- Medical History

Estimated visit time 1 hour

6.1.2 Screening visit 2 (Day 7) (+/- 7 days)

This screening visit will be conducted at the Centre for Cognitive Neuroimaging, University of Glasgow.

- Neuronavigation scan
- Motor threshold assessment
- Completion of symptom diary (to be done at home, Days 8-14)

Estimated visit time 1 hour

6.1.3 Visit 1 (Day 14) (+/- 7 days)

Visit 1 will be conducted at the Queen Elizabeth University Hospital

- 7T Neuroimaging protocol*
- Michigan Body Map Regional Pain[§]
- NRS for pain, fatigue, and depression*
- McGill Pain Questionnaire[§]
- Disease activity (SDAI / CDAI)
- Sickness Questionnaire*
- Pain confounder questionnaires[§]:
 - PROMIS-Fatigue (16-items)[§]
 - PROMIS-Depression (8 items)[§]
 - PROMIS-Anxiety (8 items)[§]
 - PROMIS-Sleep Related Impairment (8 items)[§]
 - PROMIS-Physical Functioning Short Form (8-items)[§]
 - PROMIS-Pain Interference (8-item)[§]

- ACR Fibromyalgia Scale[§]
- Venous blood sample for peripheral immunophenotyping*
- TMS or sham procedure
- Completion of symptom diary (to be done at home, Days 15-21)

**will be conducted before and after TMS/sham procedure*

§has the option to be completed remotely to reduce visit time

Estimated visit time 4 hours

6.1.4 Visit 2 (Day 28) (+/- 7 days)

Visit 2 will be conducted at the Queen Elizabeth University Hospital

- Michigan Body Map Regional Pain[§]
- NRS for pain, fatigue, and depression
- McGill Pain Questionnaire[§]
- Disease activity (SDAI / CDAI)
- Sickness Questionnaire
- Pain confounder questionnaires[§]:
 - PROMIS-Fatigue (16-items)[§]
 - PROMIS-Depression (8 items)[§]
 - PROMIS-Anxiety (8 items)[§]
 - PROMIS-Sleep Related Impairment (8 items)[§]
 - PROMIS-Physical Functioning Short Form (8-items)[§]
 - PROMIS-Pain Interference (8-item)[§]
 - ACR Fibromyalgia Scale[§]
- Venous blood sample for peripheral immunophenotyping
- Completion of symptom diary (to be done at home, Days 29-35)

§has the option to be completed remotely to reduce visit time

Estimated visit time 1.5 hours

6.1.5 Visit 3 (Day 35) (+/- 7 days)

Visit 3 will be conducted at the Queen Elizabeth University Hospital

- 7T Neuroimaging protocol*
- Michigan Body Map Regional Pain[§]
- NRS for pain, fatigue, and depression*
- McGill Pain Questionnaire[§]
- Disease activity (SDAI / CDAI)
- Sickness Questionnaire*
- Pain confounder questionnaires[§]:
 - PROMIS-Fatigue (16-items)[§]
 - PROMIS-Depression (8 items)[§]
 - PROMIS-Anxiety (8 items)[§]
 - PROMIS-Sleep Related Impairment (8 items)[§]
 - PROMIS-Physical Functioning Short Form (8-items)[§]
 - PROMIS-Pain Interference (8-item)[§]
 - ACR Fibromyalgia Scale[§]
- Venous blood sample for peripheral immunophenotyping*
- TMS or sham procedure

- Completion of symptom diary (to be done at home, Days 36-42)

**will be conducted before and after TMS/sham procedure*

§has the option to be completed remotely to reduce visit time

Estimated visit time 4 hours

6.1.6 Visit 4 (Day 49) (+/- 7 days)

Visit 4 will be conducted at the Queen Elizabeth University Hospital

- Michigan Body Map Regional Pain[§]
- NRS for pain, fatigue, and depression
- McGill Pain Questionnaire[§]
- Disease activity (SDAI / CDAI)
- Sickness Questionnaire
- Pain confounder questionnaires[§]:
 - PROMIS-Fatigue (16-items)[§]
 - PROMIS-Depression (8 items)[§]
 - PROMIS-Anxiety (8 items)[§]
 - PROMIS-Sleep Related Impairment (8 items)[§]
 - PROMIS-Physical Functioning Short Form (8-items)[§]
 - PROMIS-Pain Interference (8-item)[§]
 - ACR Fibromyalgia Scale[§]
- Venous blood sample for peripheral immunophenotyping

§has the option to be completed remotely to reduce visit time

Estimated visit time 1.5 hours

6.2 BRAIN IMAGING PROTOCOLS

6.2.1 MRI and MRS Protocols

The 7T multimodal MRI brain scanner is housed within the Imaging Centre of Excellence at the QEUH, Glasgow. An ultra-high resolution 7T multimodal MRI brain scan using a MAGNETOM Terra 7T scanner (Siemens Healthcare, Erlangen, Germany) and a single channel transmit, 32 channel receive radiofrequency head coil (Nova Medical, Wilmington, MA) will obtain neurobiological surrogate measures of structure, functional connectivity, neural signal cohesion and glutamate:

Screening (screening visit 1):

- a) **Structural MRI scan** - A whole-brain T1-weighted images will be collected using a twice magnetization-prepared rapid gradient echo (MP2RAGE) sequence, with a scanning time of 10 minutes. The scan will be processed to parcellate the brain and mark the region of interest (left IPL).
- b) **Spectroscopy voxel scan** - A magnetic resonance scan will be undertaken to identify the voxel of interest for spectroscopic imaging. A single voxel sequence will be employed with semi-LASER preparation. An approximately 20x20x20 mm³ voxel will be placed in the L-IPL, taking approximately 5 minutes.

Neuroimaging Protocol (visit 1 and visit 3):

- a) **Functional connectivity and neuronal signal cohesion data** – a resting state BOLD-fMRI scan will be undertaken. Functional connectivity MRI (fcMRI) investigations are conducted with subjects resting in the scanner. Approximately ten minutes of whole-brain resting state fMRI data

will be collected using a simultaneous-multi-slice (SMS) echoplanar- imaging (EPI) sequence of factor=4, with echo time (TE) = 25ms, repetition time (TR) = 1500ms, flip angle (FA) = 65°, field of view=192 × 192mm² with 96 slices of 1.5mm isotropic resolution. A whole-brain T₁- weighted structural image will also be collected using a twice magnetization-prepared rapid gradient echo (MP2RAGE) sequence. During the resting state, subjects will be instructed not to undertake any particular task and to stay awake with their eyes open on a fixation cross. Whole brain coverage will be performed. Data will be pre-processed and analysed using software such as statistical parametric mapping (SPM) software package version 12 (SPM12, Wellcome Department of Cognitive Neurology, London, United Kingdom) and the Conn (Cognitive and affective neuroscience laboratory, MIT, Cambridge, USA) functional connectivity toolbox, all running on MATLAB. Upon collection of resting state fcMRI data, the pre-processing steps necessary for each analysis will be included such as the removal of physiological artefacts, motion correction, realignment, registration, normalization and smoothing. Connectivity indices will be generated from matrices informed by our a priori determined regions of interest and standard grey matter atlases. Moreover, layer-dependant connectivity and network comparison will be performed.

Regarding BOLD oscillatory markers of neural signalling cohesion: Regional homogeneity (ReHo) and Amplitude of Low-Frequency Fluctuations (ALFF) are two complementary methods used to study the regional neural activity. They can be estimated using MATLAB based software such as REST (<http://restfmri.net/forum/index.php?q=rest>). The ReHo analysis is a voxel-based measure of the similarity using Kendall's coefficient concordance between the BOLD time-series of a given voxel and its nearest neighbours. The ReHo measures the synchrony of adjunct regions and can be used to evaluate the consistency of local functional activities in a brain area. While the ALFF approach measures the total power of the BOLD signal within the low-frequency range between 0.01 and 0.1 Hz. ALFF has been proven to be a valuable parameter to reflect the power of regional spontaneous neuronal activity.

b) **Glutamate Imaging** – a magnetic resonance spectroscopy scan will be undertaken in order to detect the glutamate concentration. A single voxel sequence will be employed with semi-LASER preparation. An approximately 20x20x20 mm³ voxel will be placed in the L-IPL and shimming of the static magnetic field will be performed using advanced methods best suited to MRS acquisition at 7T, such as FASTESTMAP. Spectra will be preprocessed in the MATLAB based tool MRspa, then analysed and quantified using LCModel.

In addition, experimental multi-voxel techniques will be explored to investigate the utility of quantitative maps of glutamate concentration across the brain. This will be in the form of the Accelerated magnetic resonance SPectroscopic Imaging using REadout Segmentation (ASPIRES) technique. This is a multi-voxel spectroscopic technique which has been developed in-house, building on previous work, and is based on the well-known Echo-Planar Spectroscopic Imaging (EPSI) method. ASPIRES uses readout segmentation to nullify the spectral bandwidth limitations of standard EPSI methods at 7T and undersampling schemes with advance compressed sensing reconstruction to allow for significantly shorter, clinically viable acquisition times.

c) **Layer Specific fMRI scan** - a laminar based resting-state fMRI will be collected using A C2P sequence with multiband from CMRR (University of Minnesota) with spin-echo excitation sequence. Sub-millimetre fMRI data will be analysed using BrainVoyager software. Pre-processing and analysis pipeline will include segmentation of the cortical layers, motion correction, filtering and up-sampling functional data, co-registration with anatomical data, estimation the interaction across cortical layers within the IPL and between IPL layers and other ROIs.

6.3 STUDY OUTCOME MEASURES

6.3.1 Primary Outcome Measure(s)

The primary outcome measures will be:

1. Changes in functional connectivity and neuronal signal cohesion as measured by 7T MRI
2. Changes in glutamate signal in the L-IPL as measured by 7T MRS

before and after TMS/sham procedure.

6.3.2 Secondary Outcome Measure(s)

The secondary outcome measures will be:

1. Changes in pain severity as measured by the Pain NRS
2. Changes from the Michigan Body Map Regional Pain
3. Changes in RA disease activity as measured by SDAI, CDAI
4. Changes in putative pain confounders as measured by PROMIS-Fatigue, PROMIS-Depression, PROMIS-Anxiety, PROMIS-Sleep Related Impairment, PROMIS-Physical functioning short form, PROMIS-Pain Interference and ACR Fibromyalgia Scale
5. Changes in blood protein levels of inflammatory cytokines/chemokines

before and after TMS/sham procedure (1) and (5).

before TMS/sham procedure (2), (3) and (4).

6.4 LABORATORY TESTS

Sample Type	Screening visit 1	Screening visit 2	Visit 1 [†]		Visit 2	Visit 3 [†]		Visit 4
SST tube (8.5ml)			✓	✓	✓	✓	✓	✓
EDTA tube (4ml)			✓	✓	✓	✓	✓	✓
EDTA tube (10ml x 2)			✓	✓		✓	✓	
PAXgene RNA Tube (2.5ml)*			✓	✓		✓	✓	

[†] Blood samples will be collected before and after TMS/sham procedure at these visits.

* This blood sampling will be optional at the discretion of the CI.

Blood samples will be processed and analysed as described in the Pro-BEPP Lab Protocol. Blood samples will be obtained and RNA measured for cytokines, chemokines and other proteins in order to help us measure different disturbances of the immune system in relation to rheumatoid arthritis and how they relate to the brain's pain centres.

At the end of the study, samples will be transferred to the auspices of the accredited NHS Greater Glasgow and Clyde Biorepository and stored for up to 10 years and disposed of after storage in accordance with the Human Tissue Authority's Code of Practice.

7 Study Device

Participants who are eligible for the study will receive **transcranial magnetic stimulation** using a 70 mm Double Coil connected to Super-Rapid magnetic stimulator, Magstim Co., UK. The coil and stimulator are developed and manufactured in accordance with ISO 13485:2003 and are CE marked under the Medical Device Directive (93/42/EEC).

Figure 1. Magstim Super-Rapid magnetic stimulator and 70 mm Double Coil

Further detail of the device and schedule is given below.

7.1 TRANSCRANIAL MAGNETIC STIMULATION

7.1.1 Neuronavigation Scan

As part of screening visit 2, and in preparation of the transcranial magnetic stimulation/scanning session, we will identify the optimal spot on the participants head to position the stimulation coil. For precise TMS coil positioning, TMS neuronavigation will be used (Brainsight®). This is to optimize stimulation accuracy in order to reach the area of the brain where stimulation is likely to have the best effect. To do so, the participant will be asked to wear a headband and head cap while sitting on a chair in a room. We will use an individual structural brain scan (the 7T scan performed at screening visit 1) and an optical system (camera, sensors and a digital pen) that will allow us to identify the spot on their head that is above the area in the brain that we will stimulate. We will then write on the head cap the stimulation spot, to be used in the next session. The procedure is non-invasive, painless and safe and there are no known or foreseeable risks or side effects. The TMS target site will be identified using MNI coordinates (group averaged) from our original fMRI connectivity work on RA patients.

7.1.2 Motor Threshold Assessment

Screening visit 2 will also include assessment of the resting motor threshold. This will be used to standardise the intensity of active TMS used in a subsequent session. As is normal practice, single pulse TMS will be used to stimulate the left motor cortex, which will be located with the aid of neuronavigation. The motor threshold is the minimum intensity required to elicit a motor evoked potential in the contralateral hand in at least 50% of trials. This threshold is affected by individual differences in anatomy and cortical excitability, and therefore varies between participants.

7.1.3 TMS Schedule & Administration

Active TMS will consist of a single session of 20 minutes. A figure of 8 coil will be used at 10Hz, 90% resting motor threshold intensity and 1200 pulses. The TMS pulses will be given in series of 20 trains of 6s duration (with 54s intertrain intervals).

7.1.4 Rationale for Chosen Dose

The high-frequency repetitive TMS (rTMS) protocol has been extensively used to interfere with parietal lobe network activity. In healthy participants, high frequency (10Hz) rTMS interacts with large-scale oscillatory network activity of the parietal lobe in the alpha band, causing changes in perceptual thresholds across multiple sensory modalities. Likewise, in healthy participants, high-frequency rTMS over the L-IPL reconfigures cortico-cortical network properties as revealed by fMRI. And in chronic pain patients, high frequency rTMS appears to relieve pain. Furthermore, there is evidence of analgesic efficacy in patients with fibromyalgia where high frequency rTMS has been applied to nonmotor areas.

7.1.5 Sham Procedure

Sham TMS will be applied for the exact same duration with the identical pulse sequence but using a sham TMS coil (Magstim Co., UK). This is a replica of the active figure of 8 coil and produces similar peripheral effects to the active coil (such as TMS coil clicks) but does not produce electromagnetic fields penetrating the skull.

8 RISK ASSESSMENT AND ADVERSE EVENTS

8.1 RISK ASSESSMENT

Transcranial magnetic stimulation has been used in a growing number of laboratories worldwide since 1984, however there are some potential adverse effects from TMS. Contraindications will be excluded through careful screening. All precautionary measures will be taken to avoid adverse events and safety guidelines will be rigorously followed. TMS is considered safe for studies in both healthy participants and patients when applied within the safety guidelines and is regarded as having a less than minimal risk to study participants. All contraindications and potential adverse effects will be disclosed to the participants in the Participant Information Sheet.

Common adverse effects:

Headaches and/or Neck Pain: Up to 10% of subjects undergoing TMS experience headaches or neck pain, which are believed to be due to muscle tension. All prior cases of headaches induced by TMS have promptly resolved with a single dose of paracetamol or aspirin. In some cases, TMS may cause facial discomfort on the same side of stimulation.

Hearing Problems: TMS produces a loud clicking sound when the current is passed through the stimulation coil. The peak sound pressure associated with the TMS pulse has been measured in a safety study. At a distance of 10cm and with maximum TMS intensity (100% stimulator output), the TMS pulse creates very brief (< 300 micro-sec) peak sound pressure levels of 110 dB (duration of biphasic TMS pulse: 300 micro-sec). Given that the threshold limits of impact noise would be reached only after 1'000-10'000 pulses per day (based on American Conference of Governmental Industrial Hygienists), the risk of TMS noise is considered small even without hearing protection.

Rare adverse effects:

Syncope: Fainting can occur due to anxiety and psycho-physical discomfort during testing and treatment with TMS. Subjects will be monitored for feeling any signs or symptoms of a pending syncopal event (i.e. feeling "dizzy, lightheaded or going to pass out"). If this is the case, TMS will immediately be stopped and the participant will be assisted.

Seizures: TMS can cause a seizure; however, this is an extremely rare problem. Fewer than 25 cases have been reported from the thousands of studies conducted internationally and the risk of a seizure from repeated courses of TMS is substantially less than one in a thousand. To make the participants' risk as small as possible, the investigators will follow all precautions that are recommended by the International Society for Transcranial Stimulation and mentioned in the 2008 updated safety guidelines of The Safety of TMS Consensus Group.

Memory: TMS could induce transient and weak changes in memory, attention and other cognitive and mental functions up to maximally an hour after TMS. This is a rare risk.

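### The noise-risk argument in section 8.1 does not support its conclusion: each session delivers 1,200 pulses, inside the 1,000–10,000 per day range the protocol cites as the limit

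*Protocol*

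**What the plan says.** The hearing paragraph of Protocol section 8.1, listed among the common adverse effects, describes the coil click as loud. It gives a peak sound pressure of 110 dB, measured at 10 cm and "with maximum TMS intensity (100% stimulator output". It then argues from a pulse count: the "threshold limits of impact noise would be reached only after 1'000-10'000 pulses per day", and so "the risk of TMS noise is considered small even without hearing protection".

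The dose is set elsewhere. Section 7.1.3 gives the active session as 10 Hz, "90% resting motor threshold intensity and 1200 pulses", in 20 trains of 6 s with 54 s between trains, over 20 minutes. Section 7.1.5 says "Sham TMS will be applied for the exact same duration with the identical pulse sequence", and that the sham coil "produces similar peripheral effects to the active coil (such as TMS coil clicks". Section 5.6 has each participant return three weeks later for the other procedure.

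Section 8.1 also opens with a general undertaking: "All precautionary measures will be taken to avoid adverse events and safety guidelines will be rigorously followed". No section requires ear protection for anyone, and none compares 1,200 pulses with the cited range.

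**The concern.** The inference runs from a premise about pulses per day to a conclusion about risk to unprotected ears. It needs a middle step, that the trial's daily count lies below the point at which the limit is reached. That step is missing, and the protocol's own dose contradicts it at the lower end of the range.

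This is participant-safety text. Everyone who completes both periods has two such sessions. Because the sham coil clicks too, the exposure is not confined to active stimulation. The sentence is the only place the protocol addresses hearing protection, and a reader would take from it that none is needed. Section 8.1 also says potential adverse effects will be disclosed in the participant information sheet, so the reassurance could be repeated there. That sheet is not available, and the point does not depend on it.

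**Working it through.** **Inputs**

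| Quantity | Value | Protocol section |
|---|---|---|
| Frequency | 10 Hz | 7.1.3 |
| Trains | 20 | 7.1.3 |
| Train length / gap | 6 s / 54 s | 7.1.3 |
| Stated pulses, active | 1,200 | 7.1.3 |
| Sham sequence | same as active | 7.1.5 |
| Cited noise limit | 1,000 to 10,000 pulses per day | 8.1 |
| Stimulation visits | Day 14 and Day 35, each ± 7 days | 6.1.3, 6.1.5 |

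**1. Reproduce the stated dose.**
- Pulses per train: 10 × 6 = 60.
- Pulses per session: 60 × 20 = 1,200, as stated.
- Session length: 20 × (6 + 54) s = 1,200 s = 20 min, as stated.

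**2. Pulses per day.** The nominal gap between sessions is 35 − 14 = 21 days. At the extremes of the visit windows it is (35 − 7) − (14 + 7) = 28 − 21 = 7 days. The sessions never share a day, so the count to compare with a daily limit is 1,200, not 2,400.

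**3. Compare with the cited range.**
- Against the lower end: 1,200 / 1,000 = 1.20, which is 200 pulses (20%) above it.
- Against the upper end: 1,200 / 10,000 = 0.12, or 12% of it.
- So 1,000 < 1,200 < 10,000, for active and sham alike.

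**4. When the lower end is passed.** After 16 trains, 16 × 60 = 960 pulses have been given. The 1,000th is pulse 40 of train 17, at about 16 × 60 + 4 = 964 s, or roughly 16 minutes into the 20.

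**5. Intensity.** Section 7.1.2 says "The motor threshold is the minimum intensity required to elicit a motor evoked potential". A threshold that can be measured is at most 100% of stimulator output, so active stimulation runs at no more than 0.90 × 100% = 90% of output. The sound level in section 8.1 was measured at 100%. This difference favours the protocol, but its effect on the permitted number of pulses cannot be calculated from what the protocol gives. Coil-to-ear distance during treatment is also not stated.

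**The case against.** The strongest reply is that the comparison with 1,000 pulses may not be like for like. The pulse limits follow directly from a sound level measured at maximum output, so they may apply to that case. The trial stimulates at 90% of an individual threshold, and if 1,000 is the loudest-case figure, the limit that applies here would be higher. On this view the protocol has a loosely worded justification and no demonstrated hazard.

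Part of this stands: exceedance is not shown. But section 8.1 makes no adjustment for intensity and does not say what separates the two ends of the range. The argument it makes is from pulse count, and a dose inside a range cannot be cleared by appeal to the top of that range.

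A second reply is that the sentence describes risk if protection is absent and does not instruct staff to withhold it, and that section 8.1 promises to follow safety guidelines, so ear protection may be used in practice. That is possible. The general promise names no hearing protection, however, and the more specific undertaking about the 2008 guidelines is made in the seizure paragraph to reduce seizure risk. Whether those guidelines cover hearing cannot be settled from the protocol. Neither undertaking corrects a sentence that says the risk is small without protection.

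A third reply is that asking for protection for operators goes beyond the evidence, because the hearing paragraph does not discuss them. This is fair. Extending the requirement to operators is a sensible addition, but the finding does not rest on it.

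**Conclusion.** The point holds. The planned 1,200 pulses per session day lie inside the range that section 8.1 gives for reaching impact-noise limits, 20% above the lower end and at 12% of the upper end, in both active and sham sessions. The premise therefore does not support the conclusion about unprotected ears.

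This rests only on the protocol's own dose and its own cited range, taken at face value. It does not establish that any limit is exceeded, that exposure is unsafe, or that protection would be missing in practice. The correction should be made because it concerns participant safety and costs almost nothing. Sample size, endpoints and analysis are untouched.

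**What to change.** In section 8.1, remove the clause about the absence of hearing protection and replace the inference with a statement that fits the dose, for example:

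> Each active or sham session delivers 1,200 pulses in one day, which falls within the cited range of 1,000 to 10,000. Participants will therefore wear earplugs or equivalent ear protection throughout every session.

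Add the same requirement to sections 7.1.3 and 7.1.5 so that it applies to both procedures, extend it to operators if the sponsor agrees, and check that the participant information sheet matches.

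The cost is one edited sentence, one added requirement and disposable ear protection. Used identically in both conditions, it should leave blinding and the active–sham comparison unaffected.
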